12.1 Independent Ethics Committee : Australia

The Principal Investigator is responsible for submitting this protocol to the Independent Ethics Committee. In Australia, an initial application requesting approval to conduct this study will be submitted using a National Ethics Application Form (NEAF) to a lead HREC in NSW. In addition, a review by the New South Wales Civil and Administrative Tribunal (Guardianship Division) has been completed.

Further applications will be submitted to other Independent Ethics Committees in Australia and/or to the Hospital Research Ethics Committee at each of the participating hospitals. Each application will be submitted according to the requirements of each hospital committee, all of which are formed and are conducted in accordance with the guidelines laid down by the National and Medical Research Council of Australia.

During the trial, any amendment or modification to the study protocol should be notified to the Independent Ethics Committee by the Principal Investigator and approved by the Independent Ethics Committee before implementation, unless the change is necessary to eliminate an immediate hazard to the patients, in which case the Independent Ethics Committee should be informed as soon as possible.

Each Principal Investigator will be responsible for informing the Independent Ethics Committee of any event likely to affect the safety of patients or the continued conduct of the clinical trial, in particular any change in safety.

The Principal Investigator will produce progress reports, adverse event reports, and any other required documentation to the local Independent Ethics Committee in accordance with their guidelines.

Any amendments or additions to the study protocol and material must be notified to the Independent Ethics Committee by the Principal Investigator and approved by the Independent Ethics Committee.

It is the responsibility of the Principal Investigator at each participating hospital to keep an up to date record of all correspondence and applicable documentation with the local Independent Ethics Committee.

12.2 Ethical implications of a x-cRCT design

A x-cRCT is the only feasible, practical and ethical design for this study, because of the nature of the intervention. An individual patient RCT will not be able to address the ecological effects of the intervention, whereas a 'stepped wedge' design fails to ethically address a possible harm from the therapy. A x-cRCT is essential in order to study both the patient-related direct effects of SDD (caused by the delivery of SDD to a particular patient) and indirect effects of SDD (caused to all patients by the effects of SDD on the microbiological ecology of the ICU).

As each ICU will be exposed to the study intervention for a defined time it will be possible to study secular trends in resistance in the ICUs before and after the introduction of and then cessation of SDD.

As the intervention will be offered to all eligible patients in participating ICUs as part of 'standard practice' for that ICU, recruitment for the study will be without individual patient consent. This is consistent with the NHMRC National Statement on Ethical Conduct in Human Research and the Ottawa Statement on the Ethical Design and Conduct of cRCTs.

12.3 Individual patient consent

We intend to recruit every eligible patient admitted to the study ICU during the study recruitment period.

In Australia, individual patient consent for the period of the study up to hospital discharge (the primary outcome) will not be required as a waiver of consent has been approved in Australia, subject to variation in state and institutional laws. Patients in the control arm of the trial, and the ecology surveillance periods, will be recruited without consent as no actual intervention is being offered.

12.4 Confidentiality and privacy

All patient data pertaining to the study will be stored in a computer database maintaining confidentiality in accordance with local legislation on privacy and use of health data. When archiving or processing data pertaining to the investigator and/or to the patients, the coordinating centre will take all appropriate measures to safeguard and prevent access to this data by any unauthorised third party.

The investigator will maintain the confidentiality of all study documentation and take measures to prevent accidental or premature destruction of these documents.

The investigator will retain the study documents at least fifteen years after the completion or discontinuation of the study. The investigator must notify the study management committee prior to destroying any study essential documents following the study completion or discontinuation. If the investigator's personal situation is such that archiving can no longer be ensured by him/her, the investigator shall inform the study management committee and the relevant records shall be transferred to a mutually agreed upon designee.

If any investigator retires, relocates, or otherwise withdraws from conducting a study, the responsibility for maintaining records may be transferred to the coordinating centre, or other investigator. The coordinating centre must be notified of and agree to the change. All associated documentation must also be updated.

12.5 Canadian / UK Ethics and Dissemination

12.5.1 Ethical Standard

The investigator will ensure that this study is conducted in accordance with the principles set forth in The Belmont Report: Ethical Principles and Guidelines for the Protection of Human Participants of Research and codified in the Tri-Council Policy Statement and/or the ICH E6.

12.5.2 Research Ethics Board (REB)

The protocol, informed consent form(s), recruitment materials, and all participant materials will be submitted to the REB for review and approval. Approval of both the protocol and the consent form must be obtained before any participant is enrolled. Any amendment to the protocol will require review and approval by the REB before the changes are implemented in the study, unless to eliminate an immediate hazard.

In the UK ethical approval has been awarded by an independent ethics committee according to the guidance from the NHS Health Research Authority.

12.5.3 Consent

We intend to recruit every eligible patient admitted to the study ICU during the study recruitment period.

In Canada, the laws of the jurisdiction do not allow a waiver of consent for this trial, so a delayed model consent by the substitute decision maker will be sought as soon as possible for after intervention commencement in all patients recruited into the intervention arm of the trial.

Informed consent is a process that is initiated prior to the individual agreeing to participate in the RCT and continues throughout the study participation. Given that the study intervention is time sensitive and the participant does not have capacity to provide consent, deferred consent will be used for participating sites in Canada. Deferred consent will be sought from the substitute decision maker (SDM) after the participant has been enrolled into the study and has started to receive the intervention.

Participants in both the intervention and control arms will receive an information sheet after being enrolled into the study. Initial data collection will be conducted under a waiver of consent. A member of the study staff will deliver an Information Sheet informing the SDM of the participant's enrolment into the study. The information sheet will include contact information for the SDM to reach a member of the study staff if they have any questions or do not want to participate in ongoing data collection for the study.

For participants in the intervention arm, deferred consent will be sought once an SDM has been identified. Continuous attempts (see Consent Process) will be made to approach the SDM to provide them with an informed consent form (ICF) describing in detail the study procedures and associated risks. A member of the study staff will explain the research study to the SDM and answer any questions that may arise. The SDM will sign the ICF to allow the participant to continue with the treatment. The original ICF in its entirety will be maintained by the site, and a copy of the signed ICF will be provided to the SDM. The rights and welfare of the participants will be protected by emphasizing to the SDM that the quality of the participant's clinical care will not be adversely affected if they decline to participate in this study.

If attempts to contact the SDM continue to be unsuccessful and the participant has been discharged from the ICU, or if the participant dies within 48 hours of being enrolled into the

study information recorded for the participant, along with outcome data, will be used for the study.

12.5.4 Consent Process:

- 1. As patients are enrolled into the study, an information sheet informing SDM of patient's enrolment into the study and collection of their study data will be provided.
 - a. This information sheet will also provide the SDM with information on how they can contact a member of the study team to discuss consent.
- 2. A member of the study team will review the patient enrolment log to see which patients have been enrolled/started treatment and therfore requires consent.
- 3. A member of the study team, designated on the task delegation log to obtain consent, will approach the patient's nurse to confirm if the information sheet was provided to the patient and if an SDM has been identified to be approached for consent. Alternatively, the study team member will check the patient records to identify the SDM.
- 4. The study team member will conduct regular bedside checks to find and gain consent from the SDM.
- 5. The study team member will make a minimum of 3 phone calls to the SDM if they cannot be identified at the bedside.
- 6. The study team member will document all attempts to obtain consent.

Ecology study- The requirement for consent has been waived by the REB for the ecology data collection.

In the UK, individual consent for participation in the study will be sought. However, as patients who are eligible for inclusion in the trial will lack capacity to consent, then advice about their participation will be sought from a consultee (personal or nominated) according to the Mental Capacity Act (2005). However, as initiation of the intervention is time sensitive, the intervention will be started within six hours in all eligible patients if a consultee is not available to advise. In this situation, a consultee will be approached as soon as practically possible to seek retrospective advice. Once the patient regains capacity while in hospital, s/he will be approached to seek their consent for continued participation in the study. For routinely collected anonymised clinical data (including hospital outcome data) we will not seek individual patient consent.

13 Data collection, management, and analysis

The George Institute for Global Health and Sunnybrook Research Institute are the joint trial sponsors with the George institute acting as the Principal trial co-ordination centre for the SuDDICU x-cRCT.

The George Institute will manage all aspects of data management, oversight and monitoring of data collection, co-ordination of ethical and legal clearances, co-ordination of study drug acquisition and statistical analysis for Australia. These roles will be undertaken by Sunnybrook for Canada and the UK.

The principal means of data collection and data processing will be electronic via a password protected website. All computerised forms will be electronically signed by the authorised study staff and all changes made following the electronic signing will have an electronic audit trail with a signature and date.

Folders will be provided for the research co-ordinator to file any paper documents used for any form of data collection. A comprehensive guide to the data collection with definitions and rationale will be provided together with a paper version of the data collection forms. Paper documents will be stored in secure locked cabinets with access limited to authorized persons.

A comprehensive guide to accessing the data entry forms on the website and entering all follow-up data is also provided in the guideline for case report form completion. All of these documents are also available in PDF format for printing from the study website as required. These aim to assist the research co-ordinator to ensure high-quality data collection and data entry.

13.1 Canadian Data Collection and retention

It is the responsibility of the REB, investigator and regulatory sponsor to retain study essential documents as per local regulatory requirements and GCP Guidelines.

Study essential documents must be maintained in a secure and confidential manner for participating Canadian sites for a period of 25 years. For the purposes of this study, the start date of the retention period is the date of the final report of the trial. Exceptions may be made for sites which close prematurely, wherein the start date for the retention period will be the date of notification to Health Canada of the sites closure.

Sites conducting this study outside of Canada must maintain study records for the required retention period as stipulated by local regulatory authorities. All study records are then to be destroyed according to local and national policy and requirements. It is the investigator's responsibility to request authorization for destruction at the completion of the retention period and/or for the sponsor to inform the investigator/institution when these documents may be destroyed.

14 Quality control and quality assurance monitoring

14.1 Responsibilities of the investigators

The investigators agree to perform the clinical trial in accordance with this clinical trial protocol, ICH guidelines for Good Clinical Practice and the applicable regulatory requirements. The investigators are required to ensure compliance with all procedures required by the clinical trial protocol and with all study procedures provided by the co-ordinating centre.

The investigators agree to provide reliable data and all information requested by the clinical trial protocol in an accurate and legible manner according to the instructions provided. The investigator agrees to allow representatives of the co-ordinating centre to have direct access to source documents.

14.2 Responsibilities of the co-ordinating centre

The George Institute for Global Health is responsible for taking all reasonable steps to ensure the proper conduct of the clinical trial protocol.

Prior to initiation of the study at each participating site, the co-ordinating centre will be responsible for providing adequate training to the Principal Investigator and study personnel. The training will cover all aspects of the study protocol and procedures and will include practical training in the use of the CRF website and the study materials. All study materials will be provided at or before the training sessions.

This study will be monitored by a representative of co-ordinating centre (study monitor). During the trial, the site will be contacted, through monitoring visits, letters or telephone calls, by the study monitor to review study progress, investigator and patient compliance with study protocol requirements and any emergent problems. The main duty of the study monitor is to help the investigator and the co-ordinating centre maintain a high level of ethical, scientific, technical and regulatory quality in all aspects of the trial.

Site monitoring visits will be performed periodically and in accordance with the Monitoring Plan. The investigator and study personnel will assist the monitoring staff by providing all appropriate documentation and being available to discuss the study. These monitoring visits will include but not be limited to review of the following aspects:

- 1. Adherence to the protocol including consistency with inclusion and exclusion criteria
- 2. The completeness and accuracy of the case report forms and source documentation
- 3. Patient recruitment
- 4. Adverse Event documentation and reporting
- 5. Study treatment allocation
- 6. Patient compliance with the study treatment regimen
- 7. Study treatment accountability
- 8. Compliance with regulations.

At completion of the trial, a final monitoring and close out visit will be conducted by the study monitor in accordance with the Monitoring Plan. Secure facilities for the storage of study data for 15 years will also be re-checked at this visit.

14.3 Source document requirements : Australia

According to the International Conference on Harmonisation guidelines for Good Clinical Practice, the monitoring team must check the case report form entries against the source documents. The purpose of source documents is to document the existence of the participant and substantiate the integrity of the study data collected. Source documents include the original documents related to the trial, to medical treatment, and to the history of the subject. Adequate and accurate source documents allow the investigator and the site monitor to verify the reliability and authenticity of data recorded on the electronic CRFs and ultimately to validate that the clinical study was carried out in accordance with the protocol.

14.4 Management of protocol deviations

A protocol deviation is an unanticipated or unintentional departure from the expected conduct of an approved study that is not consistent with the current research protocol or consent document. A protocol deviation may be an omission, addition or change in any procedure described in the protocol.

The investigator should not implement any deviation from or changes to the protocol without agreement by the study management committee and documented approval from the Independent Ethics Committee of the amendment, except where necessary to eliminate an immediate hazard(s) to trial participants. In the event of an emergency intended to eliminate an apparent immediate hazard to participants the Investigator may implement any medical procedure deemed appropriate.

Deviations from the protocol must be documented and promptly reported to the study management committee and the Independent Ethics Committee (if applicable). The report should summarise the event and action taken.

14.5 Direct access to data and documents

The study may be audited by government regulatory authorities, local Independent Ethics Committees or qualified representatives of The George Institute for Global Health as permitted by the regulation. Access to medical records, other source documents such as ICU charts and other study related files must be made available at all study sites for monitoring and audit purposes during the course of the study and after its completion.

Participants will not be identified by name, and confidentiality of information in medical records will be preserved. The confidentiality of the participant will be maintained unless disclosure is required by regulations.

14.6 Quality Control and Assurance: Canada

14.6.1 Site monitoring, audit and inspection

Site monitoring is conducted to ensure the safety of human study participants and the protection of their rights and well-being. Monitoring also verifies that collected study data is accurate, complete and verifiable by source documentation and that the study is conducted in accordance with the protocol and operating procedures.

Monitoring for this study is the responsibility of the sponsor. The delegated monitor will evaluate study processes and documentation based on the approved protocol/amendment(s), Part C, Division 5 of the Food and Drug Regulations, the International Conference on Harmonisation (ICH), E6: Good Clinical Practice guidelines (GCP) and institutional policies.

The extent and nature of monitoring is outlined in the Monitoring Plan. The monitoring plan specifies the frequency of monitoring, monitoring procedures, the level of site monitoring activities (e.g., the percentage of participant data to be reviewed), and the distribution of monitoring reports. Monitoring activities will be performed both in person and remotely. Reports of findings identified during monitoring activities will be provided to sites detailing any required actions. Documentation of monitoring activities and findings will be provided to the

site study team and the study QI. The institution and/or local REB reserves the right to conduct independent audits as necessary.

The Investigator is responsible for ensuring monitors and/or quality assurance reviewers are given access to all study-related documents noted above and study related facilities (e.g. pharmacy, diagnostic laboratory, etc.), and have adequate space to conduct the monitoring visit or audit.

14.6.2 Auditing and Inspecting

The investigator will provide direct access to source data/documents for the purposes of studyrelated monitoring, audits, and inspections by the REB, the sponsor, and applicable regulatory bodies. The investigator will permit the review of all study related documents (e.g. source documents, regulatory documents, data collection instruments, study data etc.) and will ensure access to applicable study-related facilities (e.g. pharmacy, diagnostic laboratory, etc.).

15 Statistical methods

15.1 Power calculation and sample size

The baseline mortality has been estimated from previous SDD studies in which a 30% hospital mortality for patients ventilated for more than 48-hours was observed in the control arm¹⁰. This was confirmed in our inception cohort pilot study where the observed mortality was 29.9% (95%CI 23.7 to 36.0%) and is consistent with the mortality of this cohort in other recent large intensive care trials.^{20,21} For the purposes of this trial we have estimated hospital mortality for our targeted patients of 29%.

The SuDDICU cRCT was originally designed to have 90% power to detect an in-hospital mortality difference of 3.5%, that is approximately half the 6% mortality difference seen in the SDD metaanalyses¹⁰ and the mortality difference observed in the most recent European SDD trial⁸. This absolute risk reduction is biologically plausible and consistent with the mortality difference seen in other large high-quality intensive care trials. The original design aimed to detect an absolute risk reduction in hospital mortality from 29% to 25.5% (3.5%), with 90% power, α < 0.05.

The inter-cluster correlation coefficient (ICC) is estimated to be 0.01. An ICC of 0.01 was observed for the previous Dutch cluster crossover study of SDD.⁷ An ICC of 0.01 has been calculated from the UK national Intensive Care National Audit and Research Centre and Australian and New Zealand Intensive Care Society Centre for Outcome Research databases.

Due to restrictions in funding in New Zealand, Canada and the UK, the original cCRT was modified to a x-cRCT conducted in Australia, assuming the same baseline mortality rate of 29% with 80% power and based on the inter-period correlation (IPC) coefficient estimated at 0.005 and sample size calculations are conservatively based on these assumptions. These assumptions are supported by data from the Australian and New Zealand Intensive Care Society ANZICS Clinical Trials Group x-cRCT PEPTIC study that reported an ICC 0.0093 and IPC 0.0072.²²

Once all sites are committed to the study, we will conduct a pre-specified validation analysis using ICC and IPC data available from the APD, for all ICU patients who either die or are ventilated for 48-hours or more, which approximates the inclusion criteria for this trial.

The current SuDDICU x-cRCT will recruit 10 000 to 15 000 patients from 19 ICUs in Australia, 7 in Canada and 3 in the UK, each recruiting at least 150 patients per period (i.e. at least 300 patients per ICU).

An analysis consisting of Australian clusters only will have at least 80% power to detect an absolute reduction in mortality of 4.2%.

An analysis consisting of Canadian and UK clusters only will have at least 80% power to detect an absolute reduction in mortality of 5.5%.

The table below shows the detectable absolute risk reduction according to the number of clusters (ICUs) and numbers of patients recruited per period.

	Average number of patients recruited per cluster per period		
	150 patients	200 patients	250 patients
Australia only (20 clusters)	4.2%	4.0%	3.8%
Australia, Canada, UK (30 clusters)	3.5%	3.3%	3.1%
Canada and UK only (10 clusters)		5.5%	

Assuming that the main ecology analyses will be performed similarly to the mortality analysis, i.e. by comparing outcome data between groups during both intervention periods, the power can be calculated assuming a cross-over design.

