6.1 Study setting

SuDDICU will be conducted in 19 general ICUs in Australia, 7 in Canada and 3 in the UK.

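### The Canada/UK claim of at least 80% power for a 5.5-point reduction needs about 200 patients per ICU-period, not the stated minimum of 150; the table also counts 20 and 30 ICUs where 19 and 29 are planned

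*Protocol*

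**What the plan says.** Protocol section 15.1 gives the planning inputs. On mortality: "For the purposes of this trial we have estimated hospital mortality for our targeted patients of 29"%. On the within-period correlation: "The inter-cluster correlation coefficient (ICC) is estimated to be 0.01". The crossover version is planned "with 80% power and based on the inter-period correlation (IPC) coefficient estimated at 0.005". The section calls these assumptions conservative and cites in support the "PEPTIC study that reported an ICC 0.0093 and IPC 0.0072". Section 15.2.1 sets a two-sided 5% level.

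On size, section 15.1 plans 10 000 to 15 000 patients, with ICUs "each recruiting at least 150 patients per period (i.e. at least 300 patients per ICU"). Section 6.1 gives the number of ICUs: "SuDDICU will be conducted in 19 general ICUs in Australia, 7 in Canada and 3 in the UK". That is 10 ICUs for Canada/UK and 29 in all.

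Two power statements follow, neither with a recruitment condition: "An analysis consisting of Australian clusters only will have at least 80% power to detect an absolute reduction in mortality of 4.2"%, and "An analysis consisting of Canadian and UK clusters only will have at least 80% power to detect an absolute reduction in mortality of 5.5"%.

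Beneath these statements, a table is indexed by the average number recruited per cluster per period (150, 200, 250). Its rows are labelled 20 clusters for Australia (4.2, 4.0, 3.8%), 30 for all regions (3.5, 3.3, 3.1%) and 10 for Canada/UK. The Canada/UK row has one entry, 5.5%, in the 200 column. The synopsis summarises the detectable reduction as 3 to 5%.

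**The concern.** The two power sentences use the same words but come from different columns of the table. The Australian 4.2% is the value at 150 per period, which is the stated minimum. The Canada/UK 5.5% is the value at 200. A claim of at least 80% power should hold at the least favourable recruitment that the plan allows, and the Canada/UK claim does not appear to. Separately, the Australian row counts one ICU more than the protocol plans.

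This matters because sections 3.2.4 and 15.2.4 commit to a separate Canada/UK analysis and publication. A non-significant result there would be read against the stated power. The synopsis range of 3 to 5% also leaves out the 5.5% given for that region.

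**Working it through.** **Inputs.** Control mortality p1 = 0.29, ICC = 0.01, IPC = 0.005 and 80% power (section 15.1); two-sided 5% (section 15.2.1); k = 19 (Australia), 10 (Canada/UK) and 29 (all); minimum m = 150 per ICU-period. Equal cluster sizes are assumed.

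**Formulas.** For a two-period cluster crossover:

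- Design effect: DE = 1 + (m − 1)·ICC − m·IPC
- Standard error of the risk difference: SE = √{[p1(1 − p1) + p2(1 − p2)]·DE/(k·m)}
- Power ≈ Φ(d/SE − 1.96), where d = p1 − p2
- Detectable difference at 80% power: the d for which d/SE = 1.96 + 0.84

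DE = 1.74, 1.99 and 2.24 for m = 150, 200 and 250.

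**Step 1: reproduce the table.** Detectable differences in percentage points at 80% power:

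| ICUs | m = 150 | m = 200 | m = 250 | Protocol |
|---|---|---|---|---|
| 20 | 4.23 | 3.92 | 3.73 | 4.2 / 4.0 / 3.8 |
| 19 | 4.33 | 4.02 | 3.82 | – |
| 30 | 3.47 | 3.22 | 3.05 | 3.5 / 3.3 / 3.1 |
| 29 | 3.52 | 3.27 | 3.11 | – |
| 10 | 5.91 | 5.49 | 5.22 | 5.5 in the 200 column |

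The protocol's figures are recovered to within 0.1 point with normal quantiles, so method and inputs match. The 5.5% is the value for 10 ICUs at 200 per period.

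**Step 2: Canada/UK power at d = 0.055** (p2 = 0.235, so the bracket is 0.2059 + 0.1798 = 0.3857):

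- m = 200: SE = √(0.3857 × 1.99/2000) = 0.0196; d/SE = 2.81; power 80%.
- m = 150: SE = √(0.3857 × 1.74/1500) = 0.0212; d/SE = 2.60; power 74%.
- m = 172 (10 000/58): DE = 1.86; SE = 0.0204; d/SE = 2.70; power 77%.
- Power reaches 80% at m = 199.

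**Step 3: Australian power at d = 0.042** (p2 = 0.248, bracket 0.2059 + 0.1865 = 0.3924):

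- 20 ICUs, m = 150: SE = √(0.3924 × 1.74/3000) = 0.0151; d/SE = 2.78; power 79%, which agrees with the stated 80% within rounding of 4.2.
- 19 ICUs, m = 150: SE = √(0.3924 × 1.74/2850) = 0.0155; d/SE = 2.71; power 77%.
- With 19 ICUs, 80% is reached at m = 169; at m = 172 power is just over 80%.

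To one decimal, 19 ICUs give 4.3/4.0/3.8 and 29 ICUs give 3.5/3.3/3.1. Correcting the counts therefore changes only the Australian entry at 150.

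**Step 4: the cited supporting values.** With ICC 0.0093 and IPC 0.0072, DE at m = 150 is 1 + 149 × 0.0093 − 150 × 0.0072 = 1.306. Power at 150 is then about 85% for Canada/UK at 5.5 points and about 88% for 19 Australian ICUs at 4.2 points.

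**Step 5: sensitivity to the reference distribution.** If the Canada/UK test used t on 8 degrees of freedom (an assumption: 10 ICUs minus 2), power at 5.5 points would be about 69% at m = 200 and 63% at m = 150.

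**The case against.** The table is headed by average recruitment, whereas 150 is a minimum for each ICU. The total target implies averages of 172 (10 000/58) to 259 (15 000/58). Over that range 19 Australian ICUs have at least 80% power for 4.2 points, if they recruit at the overall average. Canada/UK falls short only below about 199, and by about 3 percentage points of power at the bottom of the range. The inputs are also called conservative, and the correlations cited in support give more than 80% for both regions even at 150. Finally, the single Canada/UK entry may be a merged cell that was flattened when the PDF was read.

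Most of this stands, and it limits the point. It does not rescue the wording. The protocol bases its sample size on 0.01 and 0.005, those values reproduce its table, and on them the Canada/UK claim fails both at the minimum and at the average for 10 000 patients. Whatever the cell layout, 5.5% is the calculated value at 200.

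Two stronger readings are tempting and are not supported. First, a reader might see a contradiction between 29 × 300 = 8,700 patients and the 10 000 target. A total target may exceed the sum of per-site minimums, so there is none. Second, a reader might conclude from step 5 that the design ignores small-cluster inference, or that the final test will exceed its 5% level. The protocol names no reference distribution and leaves model details to a separate SAP that is not at hand. The 8 degrees of freedom are an assumption of this check.

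**Conclusion.** The Canada/UK power statement is wrong as written. On the adopted assumptions (29% mortality, ICC 0.01, IPC 0.005, two-sided 5%, normal quantiles, equal cluster sizes) it holds only from an average of about 200 per ICU-period. At the stated minimum of 150, power is about 74% and the detectable difference about 5.9 points; at an average of 172, power is about 77%.

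The cluster counts are a true but small mismatch. With 19 ICUs at 150 per period the Australian detectable difference is about 4.3 points, with 77% power at 4.2, and the shortfall disappears at about 170 per period. The combined figure remains about 3.5.

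The documents do not support saying that the trial lacks adequate power in general: under the cited correlations, normal-based power at 150 is about 85% (Canada/UK) and 88% (Australia). The degrees-of-freedom point is a caveat, not a finding.

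**What to change.** In section 15.1:

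- Restate the Canada/UK sentence as 5.5% at an average of 200 per ICU-period, and about 5.9% at 150.
- Recompute the table for 19, 29 and 10 ICUs and fill the Canada/UK cell at 150. The Australian entry at 150, and the sentence that quotes it, become about 4.3%.
- Note that the figures use normal quantiles and that a t reference with few clusters would be less favourable, and make the basis match the test method in the SAP.

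In the synopsis, align the 3 to 5% range with the Canada/UK figure of 5.5% or larger.

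Leave the 10 000 recruitment target unchanged. The cost is a text correction with slightly less favourable figures; no patients, procedures or analyses are added.
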